#### **Study Methodology (continued)**

back surgery, clinically significant back pain, clinically significant abnormal X-ray, and/or injury, that in the opinion of the investigator, would preclude CSF collection.

• Patients must visit designated imaging facilities for MRI scans for eligibility, safety and efficacy. The presence of MRI abnormalities supporting the diagnosis of MSA will also be recorded. The scans will be evaluated by a central reader, as pre-specified in the study-specific *Imaging Charter*.

At all the US sites, additional assessments (objective sensor-based assessments and qualitative Exit interviews) will be performed (hereafter referred to as the "Sensor subset" and "Exit Interview subset"). Participation in the Exit Interview subset is mandatory for patients and caregivers, while participation in the Sensor subset is optional. Patients who wish to participate in the Sensor subset must provide specific consent to one or both devices as part of the main *Informed Consent Form*. Patients can withdraw from these additional assessments without having to withdraw from the main study. Additionally, at US sites, a subset of patients and caregivers may be contacted about an opportunity to participate in a Study Experience interview ("Study Experience Interview subset").

- An independent Data Monitoring Committee (iDMC) will regularly monitor the patients' safety data according to the *Data Monitoring Committee (DMC) Charter* during the DBP.
- The study design is presented in Panel 1 and the scheduled study procedures and assessments for DBP are summarized in Panel 2 and for OLE assessments are summarized in Panel 3.

#### **Number of Patients Planned**

60 patients, recruited from specialist centres, are planned for randomization: 40 in the Lu AF82422 group and 20 in the placebo group.

#### **Target Patient Population**

Main Inclusion Criteria

- Diagnosis of possible or probable MSA-P or MSA-C according to the Gilman criteria at the Screening Visit
- Less than 5 years from the time of onset of motor MSA symptoms at the Screening Visit in the judgement of the investigator
- Anticipated survival of at least 3 years, in the opinion of the investigator, at the Screening Visit
- An UMSARS Part I score ≤16 (omitting item 11 on sexual function) at the Screening Visit
- Cognitive performance evaluated by the Montreal Cognitive Assessment (MoCA) with a score ≥22 at the Screening Visit
- The patient has a knowledgeable and reliable caregiver who will be available throughout the study when carer/observer-reported outcomes are performed. A caregiver is defined as a person who spends approximately 3 hours or more with the patient per week and can inform on level of function of the patient.
- Aged ≥40 and ≤75 years at the Screening Visit

Open-label Extension Entry Criteria

- The patient has completed the EoTDBP Visit and did not withdraw in the DBP
- The patient has consented to participate in the OLE
- The patient has completed the EoTDBP within the last 5 months and will be enrolled into the OLE no later than end of Q1 2024
- The patient is, in the investigator's opinion, likely to comply with the protocol
- The patient has not received any other investigational product since the EoTDBP Visit

#### Main Exclusion Criteria

- Treatment with an anti- $\alpha$ -synuclein monoclonal antibody (mAb) or an inhibitor of  $\alpha$ -synuclein aggregation within the last 12 months
- Any past or current treatment with an active vaccine targeting  $\alpha$ -synuclein
- The patient has two or more blood relatives with a history of MSA
- Evidence (clinically or on MRI) and/or history of any serious neurological disorder, other intracranial or systemic diseases or conditions resulting in a diagnosis other than MSA
- Current diagnosis of movement disorders that could mimic MSA; for example, Parkinson's disease, dementia

#### **Target Patient Population (continued)**

Main Exclusion Criteria (continued)

with Lewy bodies, essential tremor, progressive supranuclear palsy, spinocerebellar ataxia, spastic paraparesis, corticobasal degeneration, or vascular, pharmacological or post-encephalitic parkinsonism, per investigator discretion. Patients who have previously been diagnosed with Parkinson's disease will not be excluded

- History of severe drug allergy, anaphylaxis or hypersensitivity or known hypersensitivity or intolerance to the IMP or its excipients
- History of neurosurgical procedures including deep brain stimulation that could, in the investigator's opinion, interfere with the assessments of safety or efficacy
- Contraindications for MRI
- Attempted suicide within the past 6 months or is at significant risk of suicide (either in the opinion of the investigator or defined as a "yes" to suicidal ideation questions 4 or 5 or answering "yes" to suicidal behaviour on the C-SSRS within the past 6 months)
- The following recent and concomitant medications are disallowed or allowed with restrictions with respect to their use prior to or during the study (the list is not comprehensive):
  - *Disallowed*: any investigational products within 30 days before the Screening Visit, treatment targeting α-synuclein and/or MSA disease progression
  - Allowed with restriction: stable dose for at least 8 weeks prior to randomization of drugs acting against parkinsonism (for example Levodopa, Dopamine-Agonists, Amantadine and Monoamine oxidase b [MAO-B]
    inhibitors) and/or drugs acting against autonomic dysfunction (for example, ephedrine, droxidopa, midodrine, fludrocortisone, octreotide, desmopressin, oxybutynin) and anticipated stable during the DBP. If
    medically necessary, initiation of or change of dose of concomitant medication is allowed per investigator
    discretion.

#### Investigational Medicinal Product, Doses and Modes of Administration

Lu AF82422 is a human recombinant monoclonal antibody of the immunoglobulin G1 (IgG1) isotype that recognizes all major species of  $\alpha$ -synuclein (oligomer and fibrillar forms; N- or C-terminal truncated forms). Lu AF82422 targets extracellular  $\alpha$ -synuclein and inhibits seeding and spreading of pathological form(s) of  $\alpha$ -synuclein in *in vitro* and *in vivo* models.

#### Dosage form:

- Lu AF82422 solution for infusion 53 mg/mL, dose
- Placebo to Lu AF82422 solution for infusion

Route of administration: intravenous infusion over 30 minutes (±10 minutes) once every 4 weeks.

#### Assessment Details/Biomarker Methodology

The assessments are summarized in Panel 2 and Panel 3. Details for selected assessments are provided below. Blood and CSF assessments will be conducted using validated bioanalytical methods as specified in the *Laboratory Specification Manual*. Imaging assessments will be conducted according to the study-specific *Imaging Manual*. The scans will be evaluated by a central reader as pre-specified in the study-specific *Imaging Charter*.

#### **Efficacy Assessments**

- The UMSARS is a combined clinician and patient/caregiver-reported scale to assess disease progression in patients with MSA. The mUMSARS score will consist of UMSARS Part 1 where the response option scores of 0 and 1 will be collapsed to one category in the analysis. The aUMSARS score is derived from a subset of items from UMSARS Part I and Part II shown to be patient centric and sensitive to progression in MSA. Thus, the UMSARS will be administered only once to the patient (according to standard procedures) at the clinic visit to derive the UMSARS TS, mUMSARS and aUMSARS scores. The administration of UMSARS Part I and Part II will be video recorded for central reading.
- The COMPASS Select Change is derived from the original COMPASS scale applying a computerized algorithm. Data will be submitted to Mayo Clinic for calculations.
- MRI scan for evaluation of biomarkers of disease progression:

# Assessment Details/Biomarker Methodology (continued) Efficacy Assessments (continued)

- vMRI for quantification of atrophy measures in brain ROIs; primary ROIs: pons and cerebellum; secondary ROIs: caudate nucleus, putamen, brain stem and total grey matter
- DTI in the DBP for quantification of diffusivity measures in brain ROIs; primary ROIs: putamen, cerebellar cortex and white matter; secondary ROIs: caudate nucleus, globus pallidus and middle cerebellar peduncle
- ASL in the DBP for quantification of CBF in selected brain regions (for example, putamen and cerebellum)
- Blood sampling for biomarkers of disease progression; for quantification of NfL
- CSF sampling for biomarkers of disease progression; for quantification of t-tau and NfL
- Fall diary; assessment of Date/Time of fall; Context of fall; Causes of the fall; Consequences of the fall. Patients will receive diary training at the Randomization Visit and then start the diary data entries.
- FeetMe® sensor-based device; consists of a pair of digital insoles to be placed in patients' shoes for remote and continuous assessment of gait, which will be self-administered in the remote environment (Sensor subset).
- PAMSys sensor-based device; consists of a wearable sensor worn as a pendant on the chest and an electronic diary for a remote monitoring of falls and mobility, which will be self-administered in the remote environment (Sensor subset).
- Data from the fall diary and the Sensor subset will be collected during the Randomization period, and then for four pre-defined periods during the study according to Panel 2. The fall diary and devices will be handed out and returned at standard in-clinic visits. This does not apply to a patient who scores 4 on UMSARS Part I item 7 (walking) or if the patient is wheelchair bound for unrelated disorders. This needs to be evaluated at each visit, where the fall diary and the sensors are to be dispensed.

#### Pharmacokinetic Assessments

- Blood sampling; for quantification of "free" (that is, not bound to α-synuclein) Lu AF82422 in plasma
- CSF sampling; for quantification of "free" (that is, not bound to α-synuclein) Lu AF82422 in CSF

#### **Target Engagement Assessments**

- Blood sampling for  $\alpha$ -synuclein; for quantification of "free" and "total"  $\alpha$ -synuclein in plasma
- CSF sampling for  $\alpha$ -synuclein; for quantification of "free" and "total"  $\alpha$ -synuclein
- CSF sampling for pathological species of  $\alpha$ -synuclein (for example, aggregated and truncated species)

#### **Safety Assessments**

- MRI for safety during the DBP; for evaluation of clinically important findings for example, oedema, microhaemorrhages, infarcts and meningoencephalitis
- Blood Sampling for ADA analysis; plasma samples to determine presence or absence of ADAs. Samples confirmed positive for ADA will be evaluated for clearing ADAs by evaluation of exposure and TE.
- Adverse events requiring additional data collection: hypersensitivity reactions

#### Assessment Details/Biomarker Methodology (continued)

#### Other Study Procedures and Assessments

Qualitative semi-structured Exit interviews will be conducted via telephone or web conferencing platform (for example, Microsoft Teams) in patients and caregivers from the US sites (Exit Interview subset). The Exit interviews will take place approximately 3 weeks after the EoTDBP Visit or Withdrawal Visit. For patients withdrawing from the study, the Exit interview will only be performed if they have been in the DBP for at least 48 weeks. The interviews are tailored to the MSA population and this study in order to describe patient experience data and meaningful change (for example, symptoms, function, quality of life and disease manifestations) from the patient's and caregiver's perspective to support the interpretation of change during the study. The interviews will follow a separate interview protocol and will be conducted by ICON.

Additionally, a subset of patients and caregivers at US sites may be contacted to participate in a second semistructured interview focused on Study Experience ("Study Experience Interview subset"). The interview will include topics such as logistical considerations, satisfaction with study experience, and suggestions for improvement for future studies. The interviews will follow a separate interview protocol and will be conducted by web conferencing service (for example, Microsoft Teams) or telephone by trained interviewers from ICON. The Study Experience interview will take place after completion of the Exit interview, no later than 6 weeks after the Exit interview.

#### Statistical Methodology

- The following analysis sets will be used for the analyses:
  - all-patients-randomized set (APRS) all randomized patients
  - all-patients-treated set (APTS) all patients in the APRS who received at least one dose of double-blind IMP
  - all-patients-treated-follow-up set (APTS-FU) all patients in the APTS who complete the DBP and who
    has data collected up to or at the Safety Follow-up DBP visit
  - full-analysis set (FAS) all patients in the APTS who had a valid baseline assessment and at least one valid
    post-baseline assessment of UMSARS Part I and Part II prior to or at withdrawal from treatment in the DBP
  - PK subset (PKS) all patients in the APTS with quantifiable plasma or CSF concentration of Lu AF82422
  - sensor-based subset (SBS) all patients in the APTS who consented to wear at least one of the included sensor-based devices and who had a valid baseline assessment and at least one valid post-baseline assessment
  - exit interview subset (EIS) all patients in the FAS having a complete Exit interview with the patient
    and/or the caregiver
  - study experience interview subset (SEIS) all patients in the FAS having a complete Study Experience interview with the patient and/or the caregiver
  - open-label treatment extension set (OLES) all patients in the FAS who consented to participate in the OLE and who had at least one dose of open-label IMP for the OLE
- Since the primary, key secondary and selected secondary analyses on the UMSARS scores will be performed
  in a Bayesian framework, the success thresholds for the Bayesian posterior probability of superiority relative
  to placebo will be calibrated through simulations to correspond to a significance level of 5% evaluated
  one-sided. For the frequentist analyses, the significance level will be 5%, which will be applied one-sided. A
  testing strategy will be implemented including UMSARS TS and mUMSARS to protect the type I error for
  these two endpoints.
- The study primary estimand will be:

Study 18331A - Clinical Study Protocol

- Primary analysis: The primary efficacy analysis, that is, estimator, following up to 72 weeks of treatment will
  be based on the FAS and a Bayesian repeated measures model of the change from baseline in the UMSARS
  TS. The repeated measures model incorporates the following features:
  - · Fixed effects for change in UMSARS progression per visit
  - Participant-level random effects for the rate of UMSARS progression across visits
  - Fixed multiplicative treatment effect, θ, for increase or decrease in the overall rate of UMSARS progression of Lu AF82422 relative to placebo common across all visits. In particular, if θ<1, the active treatment slows the rate of progression of UMSARS relative to placebo. If θ>1, the active treatment increases the rate of progression of UMSARS relative to placebo. If θ = 1, the rate of progression of UMSARS is the same for both active treatment and placebo
  - Fixed multiplicative covariate effects in the increase or decrease in the overall rate of progression of UMSARS for CCI and Japan common across all visits
  - Prior distribution for model parameters selected in a conservative and non-informative manner using relatively large outcome spaces
  - Sensitivity analyses to cover model assumptions and handling of missing data applying different imputation strategies
- · Analysis of the key secondary, secondary and exploratory endpoints in the DBP:
  - · All secondary and exploratory analyses will be based on the FAS.
  - For the key secondary endpoint, that is, changes in mUMSARS from baseline up to EoT, a Bayesian repeated measures model will be applied similar to the primary analysis.
  - For changes in UMSARS Part I and UMSARS Part II scores up to EoT, a Bayesian repeated measures
    model will be applied similar to the primary analysis.
  - All remaining continuous secondary and exploratory endpoints (for example, clinical scales/assessments
    and MRI parameters) will be analyzed applying a Mixed Model for Repeated Measurements (MMRM) to
    the changes from baseline up to Week 72. If required, a log transformation will be applied for normalization. Treatment estimates will be derived for each subsequent visit. The primary comparison will be at
    Week 48, whereas Week 72 will be exploratory.
  - All categorical secondary and exploratory endpoints following 48 weeks and 72 weeks of treatment will be analyzed applying a logistic regression model. Week 48 data will be primary.
  - Number of falls per individual per fall diary period, according to the patient fall diary, will be analyzed applying a negative binomial regression model. A similar model will be applied to the falls collected by the sensor-based PAMSys device, if applicable, including data from the pre-defined periods only.
  - Additional time-to-event secondary and exploratory endpoints following 48 weeks and 72 weeks of treatment will be analyzed applying a Cox proportional-hazards model. Week 48 will be primary.
  - Lu AF82422 plasma concentrations, CSF concentrations, and the CSF/plasma concentration ratios during treatment for all patients will be presented descriptively. The data will be included in a separately reported population pharmacokinetics analysis.
  - Absolute values and changes from baseline up to Week 48 and Week 72 in blood biomarkers and Week 48 in CSF biomarkers will be analyzed descriptively. For selected parameters, a MMRM will be applied for the changes from baseline to EoTDBP. If required, a log transformation will be applied for normalization.

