The following analysis sets will be used for the analyses:

- *all-patients-randomized set* (APRS) all randomized patients
- *all-patients-treated set* (APTS) all patients in the APRS who took at least one dose of double-blind IMP
- *full-analysis set* (FAS) all patients in the APTS who had a valid baseline assessment and at least one valid post-baseline assessment of the UMSARS TS, prior to, or at withdrawal from treatment
- *PK sub-set* (PKS) all patients in the APTS with quantifiable plasma or CSF concentration of Lu AF82422
- *Sensor-based subset* (SBS) all patients in the APTS who consented to wear at least one of the included sensor-based devices and who had a valid baseline assessment and at least one valid post-baseline assessment, where 'valid assessment' covers that gait parameters can be derived within the observation period
- *Exit Interview subset* all patients in the FAS having a complete Exit interview with the patient and/or the caregiver
- *Study Experience subset* all patients in the FAS having a complete Study Experience interview with the patient and/or the caregiver
- *Open-label treatment extension set* (OLES) all patients in the FAS who consented to participate in the OLE and who had at least one dose of Open-Label IMP for the OLE

All data from the Placebo-controlled Period will be cleaned and the database for the DB-Period will be locked when there are no more patients in the DB-Period. The patients and data will be classified into the analysis sets according to these definitions at a Classification Meeting held after the database containing all efficacy measures from the DB-Period has been released but before unblinding of the study.

Demographics, baseline characteristics and baseline efficacy variables will be summarized based on the APTS and on the OLES, respectively.

The efficacy analyses for the DB-Period will be based on the FAS. Analyses for the Extension Period will be based on the OLES.

Safety outputs (including exposure and concomitant medications) will be based on APTS in the DB-Period and OLES for the Extension Period, respectively. Relevant safety outputs for data collected during the Safety Follow-up Period for participants not entering the OLE will be based on the APTS.

Listings will be based on the APTS.

6 Descriptive Statistics

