For both Baseline and the DB-Period, compliance is evaluated as number of days used for each of the two wearables, i.e., FeetMe and PanSys, which will be summarized within each interval where applied and treatment group. Furthermore, the number of patients missing 7 days or more and 14 days or more in a 28-day period will be presented by interval and treatment group. The following intervals will be evaluated:

- BL interval: V2 to V3 (2 weeks)
- Interval 1: V7 to V9 (4 weeks)
- Interval 2: V10 to V11 (4 weeks)
- Interval 3: V13 to V14 (4 weeks)
- Interval 4: V17 to V18 (4 weeks)

Records outside the above predefined intervals will be included as long as they can be mapped to one of the above intervals according to the defined visit windows (See section 24.2). Individual wearable data will be mapped to the end visit defining each interval, corresponding to the visit where the wearable is handed back.

The summaries will be based on the SBS.

13 Primary Estimand

The following primary estimand is defined as:

Proposed handling of IE's

For evaluating the appropriateness of this overall strategy, a number of sensitivity analyses will be performed using different imputation strategies for missing data. For additional information see section 14.3.5: Sensitivity Analyses of the Primary Endpoint, also covering sensitivity analyses for the key Secondary Endpoint.

Key Secondary Estimand

A key secondary study estimand will be defined in a similar manner with the endpoint of interest being the CCI

14 Efficacy

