FeetMe parameters calculated at each stride: strideLength (m), widthMotion (m), timeHeelStrike1 (ms), timeHeelStrike2 (ms), timeToeOff (ms), strideDuration (ms), velocity (m/s), cadence (stride/min), swingDuration (ms), stanceDuration (ms), swingPercentage (%), stancePercentage (%), stepTime (ms), stepLength (m), asymmetryParamStepTime (ms), asymmetryParamStepLength (m), singleSupportDuration (ms), doubleSupportDuration (ms), singleSupportPercentage (%), doubleSupportPercentage (%), asymmetryParamStrideDuration (ms), asymmetryParamStrideLength (m), asymmetryParamSingleSupportPercentage (%), strideElevation(cm), Capacitive measures of the 18 pressure sensors (in atmel unity), Centers of pressure (in cm, to confirm)

In case of large amount of missing data for a subject within a given period consisting of 10 days, the percentiles will not be derived and hence these will be set to missing. Data cleaning, population classification and confirmation of decision rules for derivation of percentiles will take place prior to database lock and will be documented as part of the classification meeting.

Additionally, raw data will be made available as sdtm format.

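### Wearable compliance in SAP 12 is summarised on a set that itself requires usable sensor data, so consenters with no valid baseline or no valid later interval are left out and the table leans upward

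*Protocol*

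**What the plan says.** SAP 12 (Wearable Compliance) states that "compliance is evaluated as number of days used for each of the two wearables", tabulated by interval and treatment group, and adds "the number of patients missing 7 days or more and 14 days or more in a 28-day period". It closes with "The summaries will be based on the SBS". No other population is named for these summaries.

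The SBS is defined in the protocol synopsis, Protocol 17.3 and SAP 5. Membership requires treatment, consent to at least "one of the included sensor-based devices and who had a valid baseline assessment and at least one valid post-baseline assessment". SAP 5 adds the meaning of validity: "where 'valid assessment' covers that gait parameters can be derived within the observation period".

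SAP 24.1.9 links recorded wear to derivability for FeetMe. "In case of large amount of missing data for a subject within a given period consisting of 10 days", the percentiles are not derived and are set to missing. SAP 24.1.10 has a softer parallel rule for PAMSys, under which endpoints may be left underived.

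Participation is optional and US-only. Under the synopsis, patients "must provide specific consent to one or both devices".

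**The concern.** A compliance table should show how far consenting patients used the device, so that a reader can judge the sensor results. Here, entry to the denominator depends on having produced enough sensor data at baseline and at least once afterwards. The patients most likely to fail that test are those who wore the device least, so the set is selected partly on the quantity being summarised.

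What is at stake is the reading of the PAMSys fall and FeetMe gait results. Nothing else in the plan reveals the loss. SAP 7.1 counts patients in each analysis set, and Protocol 17.5 does so by treatment group, but consent to a device is not an analysis set. A reader would see the size of the SBS without knowing how many consenters it left out, or from which arm.

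**Working it through.** The plan states no wearable-compliance figure, so there is none to reproduce. The check has two parts.

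**1. The chain of definitions**

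- SAP 12: the compliance denominator is the SBS.
- Protocol 17.3 and SAP 5: the SBS needs a valid baseline and at least one valid post-baseline assessment.
- SAP 5: an assessment is valid if gait parameters can be derived.
- SAP 24.1.9 and 24.1.10: parameters are, or may be, set to missing when too much of a period's data is absent.

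A consenter with too little wear at baseline, or in all four later intervals, is therefore outside the denominator. A consenter with one valid baseline and one valid later interval is inside it, and poor wear in the remaining intervals is counted.

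SAP 11 is a useful comparison. Fall diary compliance is summarised on the FAS, which depends on UMSARS data and not on diary completion. A patient with an empty diary stays in that table.

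**2. Size, by illustration**

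Let f be the share of consenters left out, C_S mean compliance in the SBS and C_R mean compliance in those left out. Then

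C_all = (1 − f) × C_S + f × C_R, and overstatement = C_S − C_all = f × (C_S − C_R).

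Every input below is an assumption. FeetMe: C_S = 8/10 = 80%. PAMSys: C_S = 20/28 = 71.4%. C_R is 0% or 25% (2.5 of 10 days; 7 of 28 days). For example, FeetMe with f = 0.20 and C_R = 0 gives 0.80 × 80% = 64.0%, an overstatement of 16.0 points.

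| Device | C_R | f = 10% | f = 20% | f = 30% |
|---|---|---|---|---|
| FeetMe, C_all (overstatement) | 0% | 72.0% (8.0) | 64.0% (16.0) | 56.0% (24.0) |
| FeetMe, C_all (overstatement) | 25% | 74.5% (5.5) | 69.0% (11.0) | 63.5% (16.5) |
| PAMSys, C_all (overstatement) | 0% | 64.3% (7.1) | 57.1% (14.3) | 50.0% (21.4) |
| PAMSys, C_all (overstatement) | 25% | 66.8% (4.6) | 62.1% (9.3) | 57.5% (13.9) |

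For the PAMSys count of patients missing 14 or more days, assume 20% in the SBS and 100% among those left out. The share among all consenters is (1 − f) × 20% + f, which gives 28%, 36% and 44% for f = 10%, 20% and 30%.

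**3. Wear period**

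FeetMe is worn for 10 days per period (Protocol 10.2.1.9, SAP 24.1.9). Against a 28-day yardstick a fully compliant FeetMe patient misses 28 − 10 = 18 days, and so counts as missing 14 or more. Any FeetMe compliance figure has to be set against 10 days.

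**The case against.** The strongest reply is that describing compliance in the patients whose sensor data are analysed is legitimate, and that the table drives no decision. PAMSys falls and FeetMe gait are exploratory, PAMSys falls are analysed descriptively and gait primarily so (SAP 14.4.2 and 14.6), and the subset is optional. This stands and sets the severity. It does not remove the selection, because SAP 12 does not present its table as conditional on usable data.

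Four stronger readings might be inferred. The documents do not support them.

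- **Everyone who did not wear the device is removed.** Only consenters with no valid baseline, or no valid assessment in any later interval, are removed.
- **The table hides fast progressors who stop wearing the sensor.** A patient with a valid baseline and first interval stays in, and later non-wear is counted. Patients scoring 4 on UMSARS Part I item 7 are not dispensed sensors by design (Protocol 10.2.1.9 and 10.2.1.10), so their lack of data is not non-compliance.
- **Patients who consented to PAMSys only are excluded because validity refers to gait.** Panel 13 of the SAP lists gait parameters among the PAMSys outputs, so such patients can qualify.
- **A given low number of days of wear is invalid.** SAP 24.1.9 gives no cut-off and leaves the rules to be confirmed before database lock.

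Some exclusions will also reflect device failure, or withdrawal before the first post-baseline interval, rather than non-wear.

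**Conclusion.** The concern holds in a limited form. SAP 12 measures wear in a set that partly requires wear, and consenters with no valid baseline or no valid later interval drop out of the table. Exclusions due to non-wear bias reported compliance upward. The bias is nil only if no one is excluded or if those excluded wore the device as well as those kept.

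The size cannot be found from the documents. About 5 to 24 percentage points follows from the assumed 10 to 30% excluded and 0 to 25% wear among them, together with the assumed SBS compliance of 80% and 71.4%; it is not an estimate for this trial.

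Severity is minor: a descriptive table, exploratory endpoints, an optional US subset, and no effect on the primary or key secondary analysis.

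**What to change.** In SAP 12:

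- Base each device's summary on all APTS patients who consented to that device and were due to be dispensed it in that interval. Leave out those not dispensed it because of a score of 4 on UMSARS Part I item 7, or because they are wheelchair bound for unrelated disorders.
- Count requested wear days without use as not worn, against each device's own period: 10 days for FeetMe; the planned 2-week baseline or 4-week interval for PAMSys. Restate the 7-day and 14-day counts to match.
- Show known device failures separately.
- Report by arm the number of consenters per device outside the SBS.
- Keep the SBS for the gait and fall results.

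Two inconsistencies should be settled in the same edit because the new denominator depends on them. SAP 12 gives intervals 2 and 3 as V10 to V11 and V13 to V14, while the schedule of assessments dispenses and returns the sensors at V11 to V12 and V14 to V15. Protocol 10.2.1.10 asks for 30 days of PAMSys wear per interval, whereas Protocol 4.2 gives 4 weeks for the treatment-period intervals and 2 weeks at baseline.

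The cost is a few sentences in SAP 12, a changed denominator and one added count. No new data are needed: PAMSys reports wear compliance (Protocol 10.2.1.10), and raw data from both devices are to be held (SAP 24.1.9 and 24.1.10). The compliance figure may look less favourable.
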